2.2. Anaesthesia plan

Preoperative :

Patients will undergo a combined spinal and epidural anaesthesia, to allow for supplementation of the anesthesia in case incomplete or insufficient blockade.

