2.2.2. Peroperative

- Monitoring :

ECG, NIBP, pulse oximetry (SpO2), peripheral venous access 18G or 16G, urinary catheter, Bair hugger.

- Realisation of the combined anaesthesia :

Vascular co-loading with 1000ml of Hartmann solution.

The patient is in a sitting position, L3-L4 level is localised. With a Vygon combined anaesthesia set, the epidural space is reached with a Tuohy 8 cm needle, 17G with a low resistance syringe filled with saline. Then, a 29G needle is used through the Tuohy needle to access to the spinal space ; once the cephalo-spinal liquid reflux is positive, the test solution with 100 µg of morphine is injected into the spinal space in approximatively 20 seconds. Then an epidural multiperforated catheter is introduced until 3-4 cm in the epidural space, an aspiration test is done but no test dose is injected. The patient is placed, after 5 minutes minimum of the intrathecal injection, in supine position with a left tilt and 3l/min of nasal O2.

Every patient receive, after randomisation, a predetermined local anaesthetic dose (bupivacaine or prilocaine).

- Nerve blockade evaluation :

The evaluation of the sensitive level will be realised by a *pressure test*, a *cold test* and a *pin-prick test*.

The block will be considered as a :

- **SUCCESS** : bilateral T4 level reached in 15 minutes after intrathecal injection without additional epidural injection needed within 45 minutes peroperative ; no pain at the skin incision, no pain during 45 minutes after the skin incision.
- **FAILURE** : level < T4 at 15 minutes after the intrathecal injection or the additional epidural injection needed during the cesarean section (*lidocaine 2% with epinephrine*) by 5ml/5minutes for a VAS< 3.

- Low blood pressure evaluation :

As low blood pressure, we define a blood pressure lower than 20% or more than the basal blood pressure (Systolic BP before spinal anaesthesia).

Treatment : *Ephedrine 5mg/ml, phenylephrine 100 µg/ml* by titration (ml by ml); blood pressure goal : Systolic BP before spinal injection -10%.

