2.4.6. Secondary effects

- Pain: VAS at incision time, placental delivery time, peritoneal closing time, skin closing time and every 5' during the c-section, then every 4 hours for 24h ;
- Nausea/ Vomiting, Headache, Prurit from 15 minutes after spinal injection, then every 4 hours for 24h ; marked as : 0= no symptoms ; 1= symptoms with no treatment necessary ; 2= Symptoms present and treated ;
- Total blood loss (ml) ;
- Transient neurologic symptoms at D0, D1, D3 and D15, Defined as pain or dysesthesia or both, showed after complete released of the block in the lower limbs (19).

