2.4.7. Post-operative analgesia

- Lifetime between the first administration of analgesic drugs after the spinal injection, doses of the administrated drugs by day et total of injections for 72h.

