2.4.9. Quality of the technic

- Time of the bladder catheterisation, time of the first miction, residual bladder volume between the end of the bladder catheterisation and the first miction, urinary retention ;
- Walking time, possibility of doing the 6MWT and the number of meters achieved, 1h, 2h, 3H and 4h after a complete recuperation of the motor block and a sensitive block below L5-S1 (after cold test and pin-prick test) ;
- Maternal satisfaction about the anesthetic technic during the surgery. It will be evaluated at the arrival in the awaking room by two methods : a) with a visual analogic scale where 0 cm = very unsatisfied and 10 cm = very satisfied ; and b) patients who have beneficiated of a previous c-section, will be asked to answer the question if they prefer the actual technic, the previous technic or have no preference (20) ;
- Maternal rehabilitation: it will be evaluated at D1, D2 and D3 in the hospitalization unit by two methods : a) with a visual analogic scale where 0 cm = very poor and 10 cm = excellent ; and b) with the QoR score (Quality of Recovery score) (20) ;
- Obstetrician and midwife satisfaction with a four points scale (0= unsatisfied/ poor quality ; 1= low satisfaction ; 2= satisfied/ good quality ; 3= very satisfied/ very good quality ; 4= excellent).
- Global cost of the technic

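### Headache is scored only to 24 hours, although every woman has a dural puncture and later assessments to D15 are already planned; headaches starting after 24 hours are not specifically recorded in either arm

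*Combined protocol and SAP*

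**What the plan says.** Headache appears in one place only, section 2.4.6 of the combined protocol and SAP, on a schedule shared with two other symptoms: "Nausea/ Vomiting, Headache, Prurit from 15 minutes after spinal injection, then every 4 hours for 24h". The grading is "0= no symptoms ; 1= symptoms with no treatment necessary ; 2= Symptoms present and treated". There is no separate definition of headache related to the puncture.

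All women have the same technique. Section 2.2 states: "Patients will undergo a combined spinal and epidural anaesthesia". Section 2.2.2 adds that "a 29G needle is used through the Tuohy needle to access to the spinal space". The Tuohy needle is taken to the epidural space; only the 29G needle is meant to pass the dura.

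Three items run beyond 24 hours:

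- Section 2.4.6: "Transient neurologic symptoms at D0, D1, D3 and D15", with the symptoms "Defined as pain or dysesthesia or both, showed after complete released of the block in the lower limbs".
- Section 2.4.9, on maternal rehabilitation: "it will be evaluated at D1, D2 and D3 in the hospitalization unit by two methods". The methods are a visual analogue scale and the QoR score.
- Section 2.4.7, on analgesics: "doses of the administrated drugs by day et total of injections for 72h".

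The documents describe no general collection of adverse events.

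**The concern.** The Introduction makes fewer side effects part of the aim of comparing the two drugs, and headache is one of the maternal effects the protocol chose to measure. Its window matches nausea and pruritus, yet the technique gives headache a possible source of its own, the dural puncture. The same section follows another possible consequence of the spinal injection, lower-limb neurologic symptoms, to D15. The plan does not explain why headache is left out of those later assessments.

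At stake is the completeness of a secondary safety result. The trial would report a 24-hour headache rate that could be taken as the headache rate of the technique. A headache on D2 or D3 could also lower a recovery score or raise the 72-hour analgesic total, with no headache item to help interpret it. Symptoms that were not asked about cannot be reliably recovered once the trial is over.

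**Working it through.** **Step 1. Compare the schedules.** The question for each item is whether a headache starting after 24 hours has a field to go into.

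| Item | Section | Time points | Records a headache after 24 h? |
|---|---|---|---|
| Headache 0/1/2 | 2.4.6 | 15 min, then 4-hourly to 24 h | No, it has ended |
| Transient neurologic symptoms | 2.4.6 | D0, D1, D3, D15 | No, lower limbs only |
| Recovery scale and QoR score | 2.4.9 | D1, D2, D3 | Not specified; QoR items are not shown |
| Analgesic doses | 2.4.7 | 72 h | Not specifically; no indication requested |

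The gap follows from the schedule and needs no assumption about onset. D1 largely overlaps the 24-hour record, so the assessments that could close the gap are D2, D3 and D15.

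**Step 2. Size.** The plan states no headache rate, onset distribution or headache sample size, so there is no figure of its own to reproduce. Its total of 100 women (section 2.1) belongs to the primary outcome. Let p be the true risk to D15 and f the share starting after 24 h. Both are assumptions.

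- Recorded per 100 = 100 × p × (1 − f)
- Missed per 100 = 100 × p × f
- Probability of missing at least one among 100 women = 1 − (1 − p × f)^100

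With p = 3%:

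- f = 30%: recorded 3 × 0.70 = 2.1, missed 0.9
- f = 80%: recorded 3 × 0.20 = 0.6, missed 2.4

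With p = 5% and f = 50%: recorded 2.5, missed 2.5, and the probability of missing at least one is 1 − (1 − 0.025)^100 = 92%.

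Over the wider grid of p from 1% to 10% and f from 25% to 75%, the expected number missed runs from 100 × 0.01 × 0.25 = 0.25 to 100 × 0.10 × 0.75 = 7.5. The probability of missing at least one runs from 22% to more than 99%.

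**Step 3. Effect on the comparison.** Let the true risks be p1 and p2, with the same f in both arms.

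- Recorded risk difference = (p2 − p1) × (1 − f), so it shrinks
- Recorded risk ratio = p2(1 − f) / p1(1 − f) = p2 / p1, so it is unchanged

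Example, assuming 5% against 10% with 50 per arm (the allocation ratio is not stated) and two-sided alpha 0.05:

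| f | Risk difference | Risk ratio | Power |
|---|---|---|---|
| 0 | 5.0 points | 2.0 | 16% |
| 0.5 | 2.5 points | 2.0 | 10% |

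Power is the usual normal approximation for two proportions. It is low with complete capture and lower with truncation.

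**The case against.** The strongest reply has four parts.

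1. **Timing is not in the documents.** They never mention headache after dural puncture, its frequency or its onset. A reader might infer that most such headaches start after the first day and that the schedule misses most of them. The documents do not support that. They show only that a headache starting after 24 hours has no specific field. This part stands in full, and every count above is therefore labelled an assumption.

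2. **The arms are treated alike.** A reader might infer that the drug comparison is biased. Sections 2.2 and 2.2.2 give both arms the same technique and needle, and section 2.4.6 gives them the same window. Nothing suggests that late headache differs by drug, and with an equal late share the risk ratio is unchanged. This also stands: what shrinks is each arm's incidence and the absolute difference.

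3. **The consequence is small.** On the 3 per 100 assumption, 0.9 to 2.4 headaches are missed in the whole trial. Headache is one of many side effects collected, the Introduction puts haemodynamic effects first, and the trial has little power for headache in any case. This limits the importance of the point but does not remove it, because a descriptive safety rate should be complete even where no test is informative.

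4. **Other items may leave a trace.** The QoR score and the 72-hour analgesic record might reflect a headache indirectly, so it goes too far to say that nothing in the data could hint at one. Neither is specified as a headache record, however, and both end by D3.

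Nor does the text say that women are seen at D15: it does not state whether that assessment is a visit or a call.

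**Conclusion.** The point holds as one about the completeness of a secondary safety item. Headache recording ends at 24 hours, and no later assessment is specified to ask about it, so headaches starting later are not specifically recorded in either arm. The recorded incidence per arm and any absolute difference are reduced by the factor 1 − f. For an assumed true rate of 3 per 100 and an assumed late share of 30% to 80%, the recorded rate is 2.1 to 0.6 per 100. Another rate or onset pattern would change these figures but not the gap.

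The finding does not extend to a bias toward bupivacaine or prilocaine, and it does not touch the primary outcome, how long the motor block takes to resolve. It is a cheap improvement worth making, not a threat to the trial's main result.

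**What to change.** In section 2.4.6, keep the 4-hourly record to 24 hours for all three symptoms. Add the existing 0/1/2 headache item at D2 and D3 (alongside the section 2.4.9 recovery assessment) and at D15 (alongside the neurologic symptoms). Word it as any headache since the last contact, with a yes/no field for whether it is worse upright. Report headache to 24 hours and headache to D15 separately, by arm, as descriptive safety results.

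The cost is one extra question at three contacts already planned, the matching fields on the case report form, and no new visit. The main drawback is recall: the D15 question looks back over about 12 days (15 − 3), so mild headaches early in that interval may be under-reported. This is a data-collection change only and alters no treatment.

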2.1. Population

Patients will be included in the study, after reading, understanding and accepting the document explaining the goals and the procedure of the study protocol and signing their consent. The study will proceed in the department of Anesthesiology-Reanimation of the CHU Saint-Pierre and in the department of Anesthesiology of the Hospital Sainte-Anne Saint-Rémi in collaboration with their respective department of obstetrics. The number of patients to be included in this study has been determined by a power study based on previous results. The trial will be end when a sample of 100 parturients will undergo a scheduled cesarean section performed with intrathécal anaesthesia.

The primary goal is to compare prilocaine with bupivacaine usually used in spinal injection; parturients will be assigned after randomisation into 2 groups:

- G1 : Hyperbaric Bupivacaine 10 mg (Marcaine®)
- G2 : Hyperbaric Prilocaine 50 mg (Tachipri ®)

To each dose will be added 2.5 µg of sufentanyl and 100 µg of morphine and the total injected volume will be identical for every group.

Inclusion criteria

- ASA < III
- Age 18-40 year
- Weight <110 kg
- Height between 160 and 175 cm
- Gestational age>37 SA
- Scheduled cesarean section
- Single fetus
- Non complicated pregnancy

Exclusion criteria

- Twin pregnancy
- History of 2 cesarean section or more
- Diabetes and gestational diabetes
- Placenta praevia

- Congenital foetale abnormality
- Patient in labour
- Membrane rupture
- Allergy to local anaesthetics
- Disagreement of the patient
- Gestational low blood pressure
- Pre eclampsia and eclampsia

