2.4. Collect of the data

2.4.1. Patients

- Name, number of file, age, weight, height, BMI, parity/gestity, ethnicity, number of previous c-section, term.
- Blood pressure, cardiac frequency, pre operatory SpO2 and before anaesthesia.
- Bladder volume before Spinal injection.

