2.4.2. Central block (spinal injection)

- Sensitive block: level (pressure test, cold and pin-prick) every 2 minutes after spinal injection for 15 minutes, then every 5 minutes until the end of the surgery, then every 30 minutes until the complete release of the sensitive block (T12-S1) ;
- Time between spinal injection and reached of T4 level ;
- Obtained level 5 minutes after spinal injection ;
- Maximum sensitive level ;
- Complete lifetime of the sensitive block (as the period between maximun level and the regression to the level T12-S2) ;
- Lifetime of an adequate anesthesia for surgery (as the period between spinal injection and a VAS \geq 3 or a sensitive level superior regressed below T4 ;
- Lifetime of the complete anesthesia (as the period between spinal injection and a VAS \geq 0.
- Motor block: Modified Bromage score (from 1 to 6), before spinal injection, 10, 15, 20 minutes after injection, then every 15 minutes until the end of the surgery, then every 30 minutes until the complete released of the motor block (Bromage 6) ;
- Time of installation of the motor block (time between spinal injection and maximum motor block or Modified Bromage score of 1) ;
- Total lifetime of the motor block (time between maximal blockade/ Modified Bromage score 1 and a Modified Bromage score 6).

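### Transient neurologic symptoms have no baseline record and no new-onset condition, so leg symptoms present before the spinal may be counted and would attenuate the comparison

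*Combined protocol and SAP*

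**What the plan says.** Section 2.4.6 has women assessed for transient neurologic symptoms on four days (D0, D1, D3, D15) and gives this definition: "Defined as pain or dysesthesia or both, showed after complete released of the block in the lower limbs". The definition carries a literature reference (19) but states no condition on the woman's state before the anaesthetic.

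The baseline list in 2.4.1 reads "Name, number of file, age, weight, height, BMI, parity/gestity, ethnicity, number of previous c-section, term", then "Blood pressure, cardiac frequency, pre operatory SpO2 and before anaesthesia", then bladder volume. It has no item for leg pain, dysaesthesia or neurological history.

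In 2.4.2 the two parts of the block are treated differently. Motor function has a pre-injection value: "Modified Bromage score (from 1 to 6), before spinal injection". Sensory testing does not: "Sensitive block: level (pressure test, cold and pin-prick) every 2 minutes after spinal injection for 15 minutes".

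The exclusions in 2.1 cover obstetric, metabolic and blood-pressure conditions, refusal, and "Allergy to local anaesthetics". None is neurological or concerns the legs. The inclusion limits on ASA class and on complicated pregnancy are general and name no such condition.

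Section 2.3 defines the primary outcome, time to motor block resolution, and ties the power of the study to that variable alone. It gives no analysis or expected rate for transient neurologic symptoms.

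**The concern.** A woman with sciatica or leg paraesthesia late in pregnancy is eligible. If she still has it when the block has worn off, she can be recorded as a case although the drug did not cause it. Nothing collected before the spinal would allow anyone to separate her from a woman whose symptoms began after the anaesthetic.

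Fewer secondary effects are part of the aim stated in the Introduction, and the bibliography includes a study of the incidence of these symptoms after intrathecal prilocaine (reference 14). The trial follows women to D15 for this item, so the count should be interpretable. If symptoms with another cause enter both arms at a similar rate, the recorded rates rise and the contrast between drugs shrinks.

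**Working it through.** **1. Is there any route by which a pre-existing symptom is identified?**

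| Place | What it records before the spinal | Pain or dysaesthesia covered? |
|---|---|---|
| 2.1, exclusions | Obstetric, metabolic, blood pressure, allergy, refusal | No |
| 2.4.1 | Demographics, obstetric history, vital signs, bladder volume | No |
| 2.4.2, motor | Modified Bromage score | No (motor only) |
| 2.4.2, sensory | Nothing stated; starts after injection | No |
| 2.4.6 | No new-onset condition | No |

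Neither component of the case definition has a baseline.

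**2. Does the wording settle it?** The verb *showed* can mean that the symptom first appeared after block release, or only that it was present then. On the second reading pre-existing symptoms are counted. On the first they should not be, but the assessor has no pre-spinal record against which to establish onset and must rely on recall. Under both readings the data cannot separate the two kinds of case.

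**3. Size, if they are counted.** The plan gives no rate for this outcome, so there is no figure of its own to reproduce. Inputs:

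- Total sample 100 (2.1). The allocation ratio is not stated; 50 per arm is assumed.
- True risks t1 and t2, and background prevalence b: all assumed. b is taken as equal in the two arms (expected under randomisation), independent of the drug effect, and persisting to the assessment.

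Formulas: observed risk p = b + (1 − b)t. Hence p2 − p1 = (1 − b)(t2 − t1), and the risk ratio is p2/p1.

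Assumed true risks of 2% and 4%. For example, at b = 5%: 0.05 + 0.95 × 0.02 = 0.069 and 0.05 + 0.95 × 0.04 = 0.088.

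| b | p1 | p2 | Risk difference (points) | Risk ratio |
|---|---|---|---|---|
| 0 | 2.0% | 4.0% | 2.0 | 2.00 |
| 5% | 6.9% | 8.8% | 1.9 | 1.28 |
| 10% | 11.8% | 13.6% | 1.8 | 1.15 |
| 20% | 21.6% | 23.2% | 1.6 | 1.07 |

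At b = 5%, the share of recorded cases with pre-existing symptoms would be 0.050/0.069 = 72% in one arm and 0.050/0.088 = 57% in the other.

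Assumed true risks of 1% and 10%, 50 per arm, two-sided 5%:

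| b | Risk difference (points) | Risk ratio | Power, normal approximation | Power, Fisher's exact test |
|---|---|---|---|---|
| 0 | 9.0 | 10 | 51% | 27% |
| 5% | 8.6 | 2.4 | 29% | 17% |
| 10% | 8.1 | 1.7 | 20% | 13% |
| 20% | 7.2 | 1.35 | 13% | 9% |

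**4. What the trial could detect without any background.** With 2% and 4% and 50 per arm, the expected counts are 1 and 2. The standard error of the difference is √[(0.02 × 0.98 + 0.04 × 0.96)/50] = 0.0341, and 0.02/0.0341 = 0.587. Power is Φ(0.587 − 1.96) + Φ(−0.587 − 1.96) = 0.085 + 0.005, or about 9%. By Fisher's exact test it is 0.6%.

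**The case against.** The strongest case against has five parts.

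- *The definition may already mean new symptoms.* It can be read that way, and the cited source may carry an onset condition that cannot be checked here. A reader might infer that pre-existing symptoms are certainly counted; the documents support only that they may be. This does not remove the gap, because even an onset rule needs a baseline to be applied.

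- *There is a neurological baseline.* In part this is right. A reader might infer that no neurological state is recorded before the spinal, but the pre-injection Bromage score would show a lower-limb motor deficit. What is missing is pain and dysaesthesia, the two symptoms that define the outcome.

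- *Randomisation protects the comparison.* It balances background symptoms on average, so neither drug is favoured systematically. It does not restore the lost contrast. The risk ratio also makes the loss look larger than the risk difference does, since the difference shrinks only by the factor 1 − b.

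- *The trial could not have shown a difference anyway.* This stands for the 2% versus 4% case. It would be wrong to infer that the missing baseline is what would hide a real difference of that size: 100 women would not reveal it with a perfect record either. At larger assumed differences, such as 1% versus 10%, the loss of power is material, though power is low to begin with. What remains in every case is that the descriptive rate for each drug may be inflated by an unknown amount.

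- *Women with a motor deficit threaten the primary outcome.* A reader might infer that a woman below Bromage 6 before the spinal could never reach the end point, and that a Bromage-based exclusion is required. The documents give no frequency for this presumably rare case, and the recorded score would identify her. The timing of randomisation is also not stated, so such an exclusion could fall after allocation. It is not needed for this point.

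**Conclusion.** The point holds as a gap in the definition and baseline of a secondary safety outcome. Lower-limb pain or dysaesthesia present before the spinal may be counted as transient neurologic symptoms and cannot be distinguished from new symptoms. The expected effect is higher recorded rates in both arms, a risk ratio closer to 1, and a risk difference multiplied by 1 − b. At assumed backgrounds of 5% to 20%, the absolute contrast loses 5% to 20% of its size, while a true ratio of 2.0 falls to between 1.28 and 1.07.

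These figures rest on assumed true risks, an assumed and unknown b, equal background in the arms and, for power, 50 women per arm. The direction does not depend on the particular values, provided that such symptoms are counted at a similar rate in both arms. The primary outcome is not affected, and nothing here indicates bias toward either drug. It is an inexpensive improvement rather than a threat to the trial's main conclusion, but a baseline not taken before the spinal cannot be reliably recovered afterwards.

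**What to change.** In 2.4.1, add an item recorded before the spinal injection: lower-limb pain or dysaesthesia, yes/no, with side and severity.

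In 2.4.6, state that transient neurologic symptoms are lower-limb pain or dysaesthesia after complete block release that is new or worse than that baseline. Including *worse* matters: a rule limited to symptoms absent beforehand would discard a woman whose existing symptoms are aggravated, and could hide a drug effect. For *worse* to be judged, severity at D0, D1, D3 and D15 should be recorded on the same scale as at baseline.

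The cost is one extra question at the existing pre-operative assessment and a severity grade at follow-ups already planned. No visit, procedure, eligibility criterion or sample size changes.
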